	3- Time elapsed till final restoration performed	Stopwatch	Continuous outcome measured in minutes

(S) Study design: Randomized controlled.

(T) Time of follow up:6 months.

8. Trial design:

Randomized controlled trial (R.C.T).

III. Methods

A) Participants, interventions & outcomes:

9. Study settings:

This study will be carried out on patients attending the out-patient clinic in Pediatric Dentistry and Dental Public Health Department-faculty of Dentistry, Cairo University, Egypt.

The procedure will be carried out by postgraduate student [name], B.D.S(2014)-Pharos University in Alexandria (PUA) and without an assistant.

10. Eligibility criteria:

Inclusion criteria:

- Children:

- 1- Aged 4 to 7, in good general health and medically free.
- 2- Cooperative patients who will comply to follow ups.
- 3- Parents provided with written informed consent.

- Teeth:

- 1- Bilaterally Carious vital primary molars with reversible pulpitis.
- 2- Restorable teeth with no more than 1/3 of root resorption.

Exclusion criteria:

- Children:

- 1- Children with medical, physical, or mental conditions.
- 2- Unable to attend follow up visits.

- Teeth:

- 1- Primary molars with any congenital anomalies.
- 2- Previously accessed teeth.
- 3- At operative procedure, haemorrhage control is unachievable after pulpotomy.

11. Interventions

The principal investigator will carry out all treatment procedures, using the split mouth technique, meaning that both groups (I & II) will be in the same patient.

For both interventions:

1. Informed consent from participating parents.
2. Baseline records photographs, percussion test, periapical radiograph, and personal data collection (Appendix 1: Diagnostic chart).
3. Allocation (concealed by withdrawing a sealed opaque envelope containing eight times folded paper containing the type of dressing material that will be used then writing patient name and ID on it and will be opened after performing the access cavity).
4. Diagnostic chart with personal, medical, and dental history will be filled (Appendix 1: Diagnostic chart).
5. Clinical examination will be performed to assess the clinical inclusion criteria. (Pulpal and periapical diagnosis is established after clinical examination).
6. Preoperative and Postoperative photographs will be taken.

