7. The radiographic examination will be performed by taking periapical x-ray using (parallel technique) through machine to assess the inclusion criteria. The preoperative radiograph will serve as a reference for the follow-up radiographs. Standardization of the technique to avoid any distortion in the vertical dimension and to provide reproducible images using x-ray holding device.
8. Preoperative and postoperative radiograph will be taken by parallel technique using XCP film holder (Super Bite, Hawe Neos Dental SA, Switzerland).
9. Administration of inferior alveolar nerve block (Septodont, Scandonest® 2% L Mepivacaine HCl. 2% and Levonordefrin 1:20,000 Injection, U.S.P.) at the side of the affected tooth.
10. Application of rubber dam for isolation, then a standardized pulpotomy procedure will be performed using a large sterile round end bur in a high-speed handpiece with copious irrigation, a sharp spoon excavator will remove pulpal tissues to the orifice level. Hemostasis will be achieved by the application of a wet cotton pellet to achieve complete hemostasis.
11. Children will then be allocated into either one of the groups alternatively depending on the pulpotomy medicament used as follows:
Group I (Experimental group) collagen based pulpotomy.
Group II (Control group) Biodentine pulpotomy.

Group I (Experimental group) collagen based Pulpotomy:

1. Collagen based pulpotomy will be applied (sterile medicated collagen particles, Biofil-AB, Eucare Pharmaceuticals Pvt. Ltd, Chennai, India) according to the manufacturer's instructions and gently placed over the pulp stumps to a thickness of 2 mm.

Group II (Control group) Biodentine pulpotomy:

1. Biodentine (Septodont, Saint-Maur-des-Fossés, France) will be applied according to the manufacturer's instructions and placed over the radicular pulp with the help of a suitable sterile amalgam carrier. Gentle condensation of the mix will be done in the pulp chamber with a moistened cotton pellet.

12. For both groups;

The rest of the pulp chamber will be filled with glass ionomer cement.

Tooth will then be restored with stainless steel crown (3M ESPE, St Paul, MN, U.S.A.).

12. Outcomes:

Primary outcome:

Absence of periapical radiolucency and internal/ external root resorption (Binary outcome detected with periapical x-ray by Parallel technique using XCP film holder (Super Bite, Hawe Neos DentalSA, Switzerland).

Secondary outcome:

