1- Survival rate (absence of any complication or complementary treatment) in terms of:

1-Absence of spontaneous pain. (Binary outcome measured with direct questioning to the patient).

2-Absence of swelling. (Binary outcome measured visually by intraoral/extraoral examination).

2- Time elapsed till final restoration performed.

13. Participant timeline:

Patients will be diagnosed to determine whether they are eligible for the inclusion criteria of this study or not.

Eligible patients will then start their treatment on the same visit.

	STUDY PERIOD					
	Enrolment	Allocation	Treatment visit	Post-treatment	Close-out	
TIMEPOINT	-t1	0	0	T1 (3m)	T2 (6m)	
ENROLMENT:						
Eligibility screen and patient selection	X					
Informed consent from participating pts	X					
Allocation (concealed in closed white envelop)	X					
INTERVENTIONS:						
The pulpotomy procedure (gaining access to the pulp)		X				
Allocation of the patient to one of the treatments groups (open the closed white envelope)		X				
Application of pulp dressing material (collagen and Biodentine)			X			
Final restoration			X			
ASSESSMENTS:						
baseline variables	1- photographs	X		X	X	X
	2- percussion test	X		X	X	X

	3- preoperative periapical radiograph	X				
	4- personal data	X				
outcome variables	Calculation of time-elapsed till final restoration			X		
	Questioning the patient about the absence of spontaneous pain	X			X	X
	Visual examination of patient to check the absence of sinus or Swelling	X			X	X
	Periapical radiograph to check the absence of periapical radiolucency, internal/ external root resorption	X		X	X	X

14. Sample size:

Sample size will be calculated.

15. Recruitment:

Patients attending the out-patient clinic in the pediatric dentistry department- Cairo University, having bilateral carious lower molars will be carefully assessed for eligibility to participate in our study by one of the main investigators [name], then a full explanation of the nature of our experiment and the importance of maintaining this primary tooth and restoring it for proper functions and the drawbacks of extracting it. Full mouth treatment will be offered for them.

B) Assignment of interventions:

16. Allocation:

16a. Random sequence generation (Randomization):

Teeth that will be included in the current trial will be randomly assigned one of the experimental groups using closed white envelopes (simple randomization 1:1 ratio).

a) Sequence generation:

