By shuffling the envelopes then selecting envelop for each patient upon their enrolment.

b) Allocation Concealment:

Using 8-time folded paper on which dressing material was written contained in the closed white envelope.

c) Implementation:

When a patient agrees to participate in the trial, an envelope will be drawn by one of the residents present at the clinic and name, telephone number and patient's ID will be written on it. Those selected envelopes will be opened at treatment visit after performing pulpotomy to choose which material should be used.

Randomization and allocation concealment will be performed by the co-supervisor to avoid selection bias.

17. Blinding:

The blinding is not possible (unfortunately) due to the nature of the trial.

Trial participants, outcome assessors and statistician will be blinded.

C)Data collection, management, and analysis:

18. Data collection methods

Baseline data collection

Plans for assessment and collection of outcomes will be at 3 and 6 months clinically (using visual examination, palpation, and percussion test with back of the mirror) and 0 and 6 months radiographically (using periapical radiograph) and will be done by two blinded assessors independently, and differences will be solved by consensus. To promote data quality, duplicate measurements by the same examiner (intra-examiner agreement) and training of assessors (inter-examiner agreement) will be done.

19. Data management:

Data will be recorded on a diagnostic chart for each patient separately and will be stored with follow up periapical radiographs.

20. Statistical methods:

Clinical and radiographic outcomes will be submitted for statistical analysis by the Statistical Package for Social Science (SPSS) program windows version 13. Results will be calculated using risk reduction (R.R.).

D) Data monitoring:

21. Monitoring

The study work results will be monitored regularly by the supervisors who will have full access to these interim results make the final decision to terminate the trial.

22. Harms

- **Bur breakage:** the bur will be replaced by a new one and treatment will be proceeded.
- **Perforation of pulpal wall or floor:** The tooth condition and size of perforation will be assessed whether the treatment will be to repair the perforation and treatment will be proceeded (the tooth will be removed from the trial) or the tooth will be extracted, and space maintainer will be performed

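### Section 11, step 11 assigns the groups 'alternatively' without mentioning the envelope; read as alternation, this conflicts with the concealed randomisation in step 3 and section 16

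*Protocol*

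**What the plan says.** The protocol describes how the material is chosen in several places.

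- **Section 11, step 11**, directly after the haemostasis step: "Children will then be allocated into either one of the groups alternatively". The sentence goes on to tie the group to the material used, and definitions of Group I (collagen) and Group II (Biodentine) follow. The envelope is not mentioned.
- **Section 11, step 3**: "Allocation (concealed by withdrawing a sealed opaque envelope containing eight times folded paper". The paper names the dressing material, and the envelope "will be opened after performing the access cavity".
- **Section 13, timeline**: a concealed envelope is listed at enrolment and its opening at the allocation time point.
- **Section 16a**: teeth are "randomly assigned one of the experimental groups using closed white envelopes (simple randomization 1:1 ratio").
- **Section 16, sequence generation**: "By shuffling the envelopes then selecting envelop for each patient upon their enrolment".
- **Section 16, implementation**: a clinic resident draws the envelope. "Those selected envelopes will be opened at treatment visit after performing pulpotomy to choose which material should be used". The stated purpose is to avoid selection bias.

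Four other statements bear on the point. Section 8 calls the study a randomised controlled trial. Section 11 opens by declaring a split-mouth design in which each child receives both materials. Sections 9 and 11 have one investigator do all the treatment, unassisted. Section 17 lists participants, outcome assessors and the statistician as blinded, but not the operator.

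**The concern.** Step 11 is the instruction that stands at the moment the material is chosen, and it is addressed to the person who places it. Taken at face value it gives a rule, alternation, that differs from the envelope. Alternation and simple randomisation cannot both determine the same assignment.

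Concealment is at stake. Section 10 excludes teeth in which bleeding cannot be controlled during the procedure, and the operator makes that judgement just before step 11. Section 16 opens the envelope only after the pulpotomy, so for the first tooth treated in a child the judgement is made without knowledge of the material. Under alternation the operator would already know it. The operator could also decide which of the two teeth to treat first, knowing which material comes next. Either route lets tooth condition become associated with material, and within-child comparison gives no protection against that.

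**Working it through.** The protocol states no figure on this point, and section 14 gives no sample size, so there is nothing to reproduce. The check sets the passages side by side and then works from definitions.

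**1. Do the passages give one rule?**

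| Feature | Section 11, step 11 | Section 11, step 3, and section 16 |
|---|---|---|
| What decides the material | Not stated; groups assigned *alternatively* | The paper inside the envelope |
| How the order arises | In turn, if read as alternation | Shuffled envelopes, one drawn per patient |
| What is assigned | Children, to one group or the other | Teeth (16a); one envelope per patient (16, sequence generation) |
| When | After haemostasis | Envelope drawn beforehand; opened after the access cavity (step 3) or after the pulpotomy (16) |

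No sentence links step 11 to the envelope. Its wording is also circular: group is said to depend on the material used, whereas under section 16 the envelope fixes the material.

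**2. What does alternation do to predictability?** In a split-mouth trial with two teeth per child there is one unknown per child, namely the material for the first tooth treated. The second tooth gets the other material.

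- Simple 1:1 randomisation: the chance of guessing the first tooth's material correctly is 1/2 = 50%, whatever went before.
- Strict alternation: once any assignment is known, the chance is 100%.
- The second tooth's material is known under either rule once the first is revealed.

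The whole loss therefore falls on the first tooth of each child. If the alternation ran tooth by tooth, with a child's two teeth treated in succession, the first tooth would receive the same material in every child, and material would be confounded with order of treatment.

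**3. Which routes to bias does this open?**

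- *Choice of which tooth is treated first*: open under alternation. It is also open under the envelope unless the tooth or side that the paper refers to is fixed before opening.
- *Exclusion of a tooth for uncontrolled bleeding*: open for the first tooth under alternation; closed for that tooth if the envelope is opened afterwards, as section 16 says.
- *Choice of which child enters*: does not by itself unbalance the groups, because each child contributes a tooth to both.

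**The case against.** The best defence is that *alternatively* is loose English for one or the other. The full sentence supports this: it continues by naming the two groups, and it neither says that children are taken in turn nor names a starting group. The envelope appears in step 3 of the same list, in the timeline and throughout section 16, and section 5 has the co-supervisor generate a random sequence. Section 16 opens the envelope at about the point where step 11 stands, so step 11 can be read as the moment when an envelope already drawn takes effect. One ambiguous adverb stands against all of this.

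Most of that stands. A reader might infer that the trial plans alternation and is therefore not randomised. The documents do not support so firm a conclusion, because the either/or reading is available and better supported. A reader might also infer that the operator could bias the comparison by choosing which children enter. The split-mouth design does not support that either.

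The defence does not make step 11 a correct statement of the section 16 rule. Even on the either/or reading it omits the envelope and sends children to a single group in a trial where each child receives both. An operator or auditor could reasonably take it as alternation.

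**Conclusion.** The point holds as a contradiction in wording that needs reconciling. Its consequence is conditional: only if step 11 were applied as alternation would concealment fail and the allocation cease to be random. In that case the first tooth's material goes from a 50% guess to certainty after the first known assignment, in the hands of an unblinded operator who also judges the haemorrhage exclusion.

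A reader might wish to turn this into a number of percentage points of bias. That would need a sample size, a difference in failure risk between better and worse teeth, and a degree of steering. The protocol gives none of these, so no such figure is offered and the point does not depend on one. It rests on two assumptions: that *alternatively* can reasonably be read as alternation, and that the operator is unblinded, as section 17's list implies. The correction should be made because it costs almost nothing and protects the validity of the comparison.

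**What to change.** Delete *alternatively* and reword step 11 along these lines: the child's sealed envelope (section 16), once opened, alone determines which of the two study teeth receives collagen; the other receives Biodentine; no alternation or other rule is used.

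The wording must name a tooth or side. An envelope that names only a material does not settle the assignment for a child who receives both. Either the paper should name the side for collagen, or the tooth to which the paper refers should be recorded before the envelope is opened. Step 3 and section 16 should give the same moment of opening as the revised step 11.

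The cost is one sentence in step 11, matching edits to step 3 and section 16, and, if the side is named, a change to what is written on the papers. Visits, procedures and assessments are unaffected.

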Pulpotomy is considered the gold standard procedure for treating cariously exposed pulps in asymptomatic primary teeth. Which is based on the healing ability of the radicular pulp tissue following amputation of the infected coronal pulp. (5)

Mineral trioxide aggregate (MTA) has been recommended as the gold standard for vital pulp therapy; however, it has some disadvantages, such as long setting time, poor handling properties, high cost, and the potential for tooth discoloration. Biodentine (Septodont, Saint-Maur-des-Fossés, France), one of the new-generation, bioactive endodontic cements, has been claimed to have improved properties over MTA.

Biodentine presents high biocompatibility with the dental pulp, it has high antibacterial effects and antifungal activity, has a shorter setting time than MTA as a result of the calcium chloride in the liquid component of Biodentine. It also has higher flexural strength, compressive strength and modulus of elasticity than MTA. Consequently, Biodentine can be used as a pulp dressing as well as a base material. (6)

Quest is on for newer pulpal medicaments that are biocompatible and capable of healing the dental pulp by producing reparative dentin and/or dentinal bridge in response to various stimuli and surgical exposure.

Collagen has a proven rate of success in the field of dentistry as guided tissue regeneration, root conditioning, hemostatic, and wound dressing agent. It has inherent properties like low immune response and toxicity, ability to promote cellular growth and attachment, homeostasis, and added advantage of antibiotic incorporation. (7)

7. Objectives:

Aim of the study

To assess clinical and radiographic success after collagen based pulpotomy versus Biodentine pulpotomy in children with cariously exposed vital primary molars.

Hypothesis:

Null hypothesis: No added benefits will be gained from the collagen based pulpotomy clinically and radiographically.

PICO approach:

P: Population: Children 4-7 years with carious vital primary molars.

I: Intervention: Sterile medicated Collagen particles.

C: Control: Biodentine.

O: Outcome:

Outcome		Method of measurement	Unit
1ry outcome: Clinical success	1- Absence of internal root resorption	Periapical X-ray (parallel technique)	Binary
2ry outcome:	1- Absence of pain	Questioning the patient	Binary
	2- Absence of swelling	Visually by intraoral and extraoral examination	Binary

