The investigator will be given access to data sets. All data sets will be password protected. To ensure confidentiality, data dispersed to project team members will be blinded of any identifying participant information.

30. post-trial care:

The investigator will offer full mouth treatment, post-operative care, and preventive measures to all participants.

31. Dissemination policy:

The Thesis defense will be done as the study is a part of the requirements for a master's degree in Pediatric Dentistry. Also, the results of the study will be published in Journals.

V. Appendices**Appendix 1: Chart filled for each patient in this trial:**

Patient name:

Patient ID:

Tested material:

Age:

sex:

Address:

Telephone:

Chief complain of the patient:

Pretreatment medications:

Participating tooth:

Date of material application:

Follow up		1ry outcomes assessment clinical assessment (survival rate)		2ry outcomes assessment Radiographic assessment			Final assessment “success or failure”
Time after	Date	1- Spontaneous pain	2- Swelling	3- Internal root resorption	4 - External root resorption	5- Periapical radiolucency	
3m	/ /20						
6m	/ /20						

VI. References:

- 1- izGuven SD. *Success Rates of Pulpotomies in Primary Molars Using Calcium SilicateBased Materials: A Randomized Control Trial. Biomed Res Int.* 2017;2017:7.
- 3- *Use of collagen as a biomaterial: An update - researchgate. (n.d.). Retrieved March 6, 2022, from* https://www.researchgate.net/publication/258204888_Use_of_collagen_as_a_biomaterial_An_update
- 5- J. Camilleri. “Hydration characteristics of biodentine and theracal used as pulp capping materials.” *Dent Mater.* 2014;30:709–715.

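### The primary outcome is defined in three conflicting ways, in section 7, section 12 and the Appendix 1 chart

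*Protocol*

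**What the plan says.** The primary outcome is designated in three places.

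- **Section 7 (Objectives, PICO outcome table).** The row is labelled "1ry outcome: Clinical success", but its only content is "Absence of internal root resorption", measured on a periapical X-ray. Pain, swelling and time to final restoration are secondary.
- **Section 12 (Outcomes).** The primary outcome is "Absence of periapical radiolucency and internal/ external root resorption", binary and read on a periapical film. Pain and swelling are secondary, grouped as "Survival rate (absence of any complication or complementary treatment) in terms of" those two signs. Time to restoration is also secondary.
- **Appendix 1 (follow-up chart).** The columns for spontaneous pain and swelling stand under "1ry outcomes assessment clinical assessment (survival rate". Those for internal resorption, external resorption and periapical radiolucency stand under "2ry outcomes assessment Radiographic assessment". A last column, "Final assessment", records success or failure with no rule for deriving it.

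The chart is the trial's data record. Section 19 says: "Data will be recorded on a diagnostic chart for each patient separately".

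On timing, section 7 gives a 6-month follow-up. Section 13 schedules the outcome radiograph at 3 and 6 months, and the chart has radiographic columns in its 3-month row. Section 18 lists radiographs at 0 and 6 months only.

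**The concern.** A trial needs one primary outcome, fixed before the data are seen. Here two sections give radiographic definitions of different scope, and the data form gives primary status to a different domain, clinical signs. The chart collects all five signs, so any of the three definitions can be applied to the same completed forms. The choice could then be made with results in view, and section 21 gives the supervisors full access to interim results.

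The sample size is also affected. Section 14 leaves it to be calculated, and that calculation needs the expected rate of one named endpoint. Three endpoints with different content need not share a rate. Section 20 does not help, because it ties its effect measure to no particular outcome.

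**Working it through.** The protocol states no sample size, success rate, alpha or power, so there is no figure to reproduce. The check is logical: write each statement as a rule, then apply the rules to teeth that show exactly one of the chart's five signs.

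**Rules for failing the primary outcome**

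- Section 7: internal resorption present.
- Section 12: internal resorption, external resorption or periapical radiolucency present.
- Chart, read from its primary heading: pain or swelling present.

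**Primary verdict for a tooth with one sign only**

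| Sign | Section 7 | Section 12 | Chart |
|---|---|---|---|
| Internal resorption | Fail | Fail | Success |
| External resorption | Success | Fail | Success |
| Periapical radiolucency | Success | Fail | Success |
| Pain | Success | Success | Fail |
| Swelling | Success | Success | Fail |

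**Counts**

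- All three agree: 0 of 5.
- Section 7 against section 12: 2 of 5 differ (external resorption, radiolucency).
- Section 7 against the chart: 3 of 5 differ (internal resorption, pain, swelling).
- Section 12 against the chart: 5 of 5 differ.

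A tooth with pain or swelling alone still fails a secondary outcome in sections 7 and 12. The table concerns the primary verdict only.

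**Could PDF extraction explain the chart headings?** No. The table layout is flattened, but the primary heading itself names the clinical assessment and survival rate, and the secondary heading names the radiographic assessment. Section 12 defines survival rate by pain and swelling, and lists it as secondary.

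**Timing.** Six months is implied as the primary time point by the follow-up line in section 7 and by sections 13 and 18, but the outcome wording does not state it. The 3-month radiograph is a direct conflict: section 13 and the chart include it, and section 18 does not.

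**Resorption at entry (a lesser point).** Section 10 admits teeth with up to one third root resorption, while section 12 asks for the absence of external resorption. Section 11 names the preoperative film as the reference, which suggests a comparison with baseline, but the outcome wording does not carry this through.

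**The case against.** The strongest reply is that the text mostly points to one definition. Internal resorption is a component of the section 12 composite. Sections 7 and 12 both use the periapical film and both keep pain, swelling and time secondary. Section 13 repeats the three signs of section 12. On this reading, section 7 is an abbreviated and mislabelled row and the chart headings are simply transposed. The chart states no explicit primary rule, and it records every sign separately, so no data are lost.

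Part of this stands. Sections 7 and 12 do agree on domain, transposed headings are plausible, and the chart rule used above is inferred from a heading. The 5 of 5 count follows automatically from comparing two sets of signs that do not overlap and together cover all five. None of the counts measures how often a verdict would change in practice.

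It does not remove the conflict. Nesting still changes the primary verdict for a tooth with only external resorption or only a radiolucency, and section 7 lists no other primary sign. Nothing in the protocol establishes that the headings are an error. Keeping all five signs is what lets several primary results be drawn from the same forms.

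A second reply is that the rule for the final column, the reading criterion for resorption and a baseline row could sit in a statistical analysis plan. That is fair, and those are minor additions here. The choice of primary outcome is different, because the protocol itself fixes it in contradictory ways. The 3-month film is a scheduling conflict that does not alter which signs are primary at 6 months, but it is real.

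**Conclusion.** The concern holds. The protocol designates three different primary outcomes and gives no order of precedence. No single-sign tooth receives the same primary verdict under all three, and the pairwise disagreements are 2, 3 and 5 of 5.

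The comparison of sections 7 and 12 rests on their wording alone. The two comparisons with the chart also assume that its primary heading means what it says. No event rates are assumed, and no effect on sample size or false-positive risk is quantified, because both depend on rates, tests and effect patterns that the protocol does not give.

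This needs correcting before the sample size is calculated and before any outcome is recorded on the chart.

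**What to change.** 1. State one primary outcome at 6 months, in identical words, in section 7, section 12 and Appendix 1. The section 12 composite is one candidate, since section 13 already repeats its three signs.
2. Correct the clinical label on the radiographic row in section 7 and the primary and secondary headings on the chart. If the composite is kept, pain, swelling and time stay secondary throughout.
3. State how the final column of the chart is derived, or remove it.
4. Word the radiographic outcome relative to the preoperative film that section 11 already names as the reference. The investigators set and write down the reading criterion for resorption present at entry. A baseline radiographic row on the chart, which now has only 3-month and 6-month rows, would hold that reading.
5. Reconcile section 13, section 18 and the chart on the 3-month radiograph.
6. Then calculate the sample size for the chosen outcome.

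The cost is wording in sections 7, 12 and 13 or 18, the chart headings, one line for the final column, one baseline row and one written reading criterion. No visit is added, and no film beyond those section 13 already schedules. Whether the 3-month film is taken depends on how item 5 is settled.
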